## 6.2 DESCRIPTION OF CLINICAL INVESTIGATION PHASES

### 6.2.1 Inclusion phase (Visit 1)

Following approval by the ethics committee and any required competent authority, the subject will be screened for study eligibility and a signed informed consent will be obtained.

Once the patient has signed the approved ICF and has met all the inclusion and no exclusion criteria, the subject will be considered eligible to be enrolled in the study.

If the subject does not meet the PD prescription requirement, the subject may consent to participate in the study and to a change of PD prescription in order to meet the requirement. A run-in period of at least two weeks with a PD prescription that meets the inclusion criteria will then be performed.

After the run-in period physician will review the eligibility of the patient to continue the study and complete the inclusion of the patient (enrolment point) **or** alternatively exclude the patient from the study. The exclusion of the patient will be recorded as a screening failure and will not be further followed up in the study.

Patient demographics, medical history, concomitant medications, baseline PD prescription and 24-hour UF volume will be recorded. A screening log will be maintained at each study site containing limited non-identifiable information.

During the inclusion phase the subject will, together with the responsible physician, decide during what day of the week and what time of the day the efficacy evaluation treatments will be performed. All efficacy evaluation treatments should be performed the same day of the week and the same time of the day. In order to perform the 2.27% glucose comparator dwell and the Carry Life® UF treatment at the same time of day, the physician may need to modify the order and duration of the CAPD day dwells during the efficacy evaluation days in the control arm of the home treatment phase of the study.

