METHODOLOGY	
The study consists of the following five (5) phases:
 

1. Inclusion phase.

2. In-clinic treatment phase for dose determination and safety evaluation.

3. Randomization phase.

4. Transition to home treatment phase.

5. Home treatment phase for efficacy and safety evaluation.

 
CAPD patients need to use the Baxter PD system and have a PD prescription of at least one 1.5-2.0 L 2.27% glucose day dwell to be included in the study. Throughout the study, the subject will use the fill volume they normally use, both for the standard PD prescription and for the Carry Life® UF treatments. However, for the peritoneal equilibrium test (PET), a 2 L fill volume will be used.
 
The in-clinic phase consists of one 2.27% CAPD dwell and two Carry Life® UF treatments; one with a 11 g/h glucose dose and one with a 15 g/h glucose dose. The Carry Life® UF treatments will be used for a safety evaluation and based on the UF volumes achieved with the Carry Life® UF treatments, the Carry Life® UF glucose dose for the home treatment phase will be determined.
 
After completion of the in-clinic treatment phase, subjects will be randomized to start the home treatment phase either with the control treatment arm or with the Carry Life® UF treatment arm. Subjects in the control arm will continue their standard CAPD treatment as prescribed. In the Carry Life® UF arm, for three days of the week one 2.27% glucose CAPD dwell per day will be replaced by a Carry Life® UF treatment. For the remaining four days of the week, one 2.27% glucose CAPD dwell will be replaced with a 1.36% glucose CAPD dwell.
 
Immediately before the subject starts using the Carry Life® UF device at home, there will be a transition to the home treatment phase during which the patient will be trained in how to use the Carry Life® UF system.
 
AEs, SAEs, and Carry Life® UF device malfunctions will be recorded throughout the study. A nurse at each participating clinic who has undergone education and training necessary for thorough AE collection will be responsible for the recording of AEs i.e., education in Good Clinical Practice (GCP) will be required and training with respect to the electronic case record form (eCRF) for AE reporting. In case of an AE or Carry Life® UF device malfunction during the home phase, the subject will be instructed to immediately contact the clinic. Furthermore, the clinic will contact the subject weekly and specifically ask about the occurrence of any AE or Carry Life® UF device malfunction.
 
Any changes in medications or PD prescriptions will be recorded during the study. If changes to diuretic prescription or PD prescription are made, the reason for the change will be documented. If a study participant discontinues the clinical study the reason for this will be documented in detail.

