### 6.1 GENERAL

The clinical investigation is a pre-market, prospective, multicenter, randomized, crossover study in adult subjects with ESKD treated with CAPD.

The study consists of the following five phases:

1. Inclusion phase.
2. In-clinic treatment phase for dose determination and safety evaluation.
3. Randomization phase.
4. Transition to home phase.
5. Home treatment phase for efficacy and safety evaluation.

Patients need to use the Baxter PD system and have a PD prescription of at least one 2.27% glucose day dwell of 1.5-2 L to be included in the study. There is an optional run-in phase during the inclusion phase in order for the patient to meet the PD prescription inclusion criteria. Throughout the study, the subject will use the fill volume they normally use, both for the standard PD prescription and for the Carry Life® UF treatments. However, for the PET a 2 L fill volume will be used.

The in-clinic phase consists of one 2.27% CAPD dwell (PET) and two Carry Life® UF treatments (one at 11 g/h glucose and one at 15 g/h glucose). The Carry Life® UF treatments will be used for a safety evaluation, and based on the UF volumes achieved, the Carry Life® UF glucose dose for the home treatment phase will be determined.

After completion of the in-clinic phase, subjects will be randomized to start the home treatment phase either with the control treatment arm or with the Carry Life® UF treatment arm. Subjects in the control arm will continue their standard CAPD treatment. In the Carry Life® UF arm, one 2.27% glucose CAPD dwells per day will at three days of the week be replaced by a Carry Life® UF treatment. During the remaining four days of the week, one 2.27% glucose CAPD dwell will be replaced with a 1.36% glucose CAPD dwell.

The Carry Life UF system will be used during Mondays, Wednesdays and Fridays, instead of a 2.27% glucose dwell. The time of the day when the Carry Life® UF system will be used does not need to be at the same time of the day as the 2.27% glucose dwell. The time of the day when the Carry Life UF system will be used, may differ on different days based on the subject's schedule.

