### 6.3 SUBJECTS

#### 6.3.1 Subject selection

The patients to be recruited in the clinical investigation have been on stable PD therapy for ESKD for at least three months and with a PD prescription of 2-4 CAPD dwells/day, unchanged for a minimum of two weeks, with at least one 1.5-2 L 2.27% glucose day dwell daily.

Should a change of the PD prescription be necessary for a subject to be eligible for the study, a run-in period of at least two weeks with the modified PD prescription should take place. The change in prescription will be made after assessment by the responsible physician to ensure that the new prescription is clinically comparable to the current prescription. Such a change will require the subject to consent to a change of PD prescription on the Patient Informed Consent Form. After the run-in period physician will review the eligibility of the patient to continue the study and complete the inclusion of the patient (enrolment point) **or** alternatively exclude the patient from the study. The exclusion of the patient will be recorded as a screening failure and the subject will not be further followed up in the study.

If patients treated with PD therapies have regular clinical checkups the Investigator may either approach the patient during these visits or by other means. After the patient has signed the ICF they are allocated a specific study number, which is used in the investigation documents and consecutive number are allocated with continued inclusion at each site.

Approximately 25 patients will be enrolled in this clinical investigation with a goal of 19 completing the study per protocol. Patients will be enrolled across six (6) to twelve (12) European sites.

There will be a competitive enrolment without a minimum enrolment for each site.

All patients recruited in the clinical investigation shall be accounted for, including those who withdraw from the investigation. The total duration of the patient's participation is around 12 weeks depending upon when it is suitable for the patients to schedule the study visits. The total time for recruitment and study completion is estimated to be approximately 12 months (including an estimated 9-month enrolment period).

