#### 6.4.1 Clinical investigation related procedures

##### Visit 1: Screening and inclusion (-14–0 Days)

The activities are mainly concerned with the collection of the informed consent and baseline data as follows:

1. Fulfillment of the Inclusion and exclusion criteria (enrolment point).

2. Demographics (year of birth, age, gender, ethnicity, height, and body weight).
3. Medical history (including, cause of ESKD, year of diagnosis of kidney disease, start of PD, start of ESKD therapy other than PD, if applicable, and comorbidities).
4. Concomitant medications.
5. Baseline PD prescription (volumes and glucose concentration for the day dwells, volume for the icodextrin and volume and glucose concentration for glucose-based night dwell, as applicable).
6. Fluid restriction.

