#### Timelines:

Any AE/SAE/SADE that occur after the subject has been enrolled until study completion/ termination must be reported to the Sponsor **immediately, but not later than 3 calendar days** after investigational staff become aware of the event. All DDs involving any device component must be **reported within 24 hours** of staff become aware of the event to Triomed and the medical device handled according to Section 14.3.

Particular attention shall be given to the causality evaluation of USADE events. The occurrence of unanticipated serious adverse events related to the use of the device (USADE) could suggest that the clinical investigation places subjects at increased risk of harm than was to be expected beforehand. All USADE must be reported to the Sponsor regardless of severity **within 24 hours**.

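### For run-in subjects, AE/SAE reporting to the sponsor starts only at enrolment, after at least two weeks on a prescription changed for eligibility, and those then excluded are not followed

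*Protocol*

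**What the plan says.** **The run-in.** Section 6.1 states that "There is an optional run-in phase during the inclusion phase". Under Section 6.2.1, where a patient does not meet the prescription requirement, "the subject may consent to participate in the study and to a change of PD prescription in order to meet the requirement". Then follows "A run-in period of at least two weeks with a PD prescription that meets the inclusion criteria". Section 6.3.1 gives the same purpose: "Should a change of the PD prescription be necessary for a subject to be eligible for the study". It adds that the responsible physician assesses whether the new prescription is comparable in clinical terms to the current one.

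**Enrolment.** After the run-in the physician reviews eligibility and may "complete the inclusion of the patient (enrolment point"), or else exclude the patient. Sections 6.2.1 and 6.3.1 both class an excluded patient as a screening failure with no further follow-up in the study.

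**Adverse events, with a start.** The timelines in Section 14.4.2 require reporting to the sponsor within 3 calendar days and cover "Any AE/SAE/SADE that occur after the subject has been enrolled". Table 12 sets the same start for SAEs. In Table 1 the AE row is empty at V1 and begins at V2-V4. The Visit 1 list in Section 6.4.1 has no AE item, while the lists for all later visits do.

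**Adverse events, without a start.** The synopsis says "AEs, SAEs, and Carry Life® UF device malfunctions will be recorded throughout the study", and Section 6.1 says much the same. Section 14.4.1 has the site record each AE in the medical notes and eCRF and follow it to resolution or stabilization. Section 14.5 has the investigator record and monitor all safety events.

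**Timing.** Visit 1 is headed "Screening and inclusion (-14–0 Days"). Participation is given as about 12 weeks.

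**The concern.** These patients have consented to the trial, and their dialysis prescription has been altered so that they can enter it. The time is not ordinary pre-screening observation, because any harm from the change is a consequence of taking part. The rules that tell a site when to report begin only once that period is over.

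Two things are at stake. First, an AE or SAE arising from the change may never reach the sponsor. Section 14.6.1 makes an SAE with a causal link to the investigation procedure reportable to the authorities, and Section 14.7.2 counts procedures specific to the investigation. If the eligibility-driven change is such a procedure, the sponsor may owe a report on an event of which no dated rule requires the site to inform it. Second, a subject excluded because of such an event leaves follow-up, although Sections 6.3.2.1 and 14.4.1 require AEs ongoing at withdrawal to be followed until resolved or stable. Sites could reasonably act differently on the same text.

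**Working it through.** **1. When reporting starts for a run-in subject.** The order of events in Sections 6.2.1 and 6.3.1 is: consent, prescription change, run-in of at least 14 days, eligibility review, enrolment.

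| Place in protocol | Duty | Start given |
|---|---|---|
| 14.4.2, timelines | Report AE/SAE/SADE to sponsor | Enrolment |
| Table 12 | Report SAE to sponsor | Enrolment |
| Table 1 | AE/SAE row | V2-V4; blank at V1 |
| 6.4.1, Visit 1 | Activity list | No AE item |
| 14.3 | Investigator reports reportable events to sponsor | None; refers on to later sections |
| 14.4.1 and 14.5 | Record every AE / all safety events | None |
| Synopsis and 6.1 | Record or collect AEs during the study | None |
| 14.2 | Give site contacts for AE reporting | At ICF signature; contacts only |

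Every place that dates AE reporting or schedules AE collection starts after the run-in. The places that could cover the run-in set no start. The period between consent and mandatory reporting is therefore at least 14 days, with no upper limit. Inclusion criterion 3 needs a prescription unchanged for at least two weeks, so the minimum cannot be shortened.

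**2. What happens to subjects excluded after the run-in.** They are screening failures without further follow-up. They are not included patients, so they fall outside the ITT population (Section 7.1.2). They have had no device treatment, so they fall outside the safety population (Section 7.1.3). No analysis set picks up their events.

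**3. Effect on the safety endpoint.** Section 7.1.7.1 presents AE and SAE rates for the Carry Life UF arm and the control arm of the home phase, in events per day. Run-in events precede randomization and belong to neither arm, so those rates do not change.

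**4. The Visit 1 window (minor).** Slack = window − run-in length.

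- 14-day run-in: 14 − 14 = 0 days. It fits only if consent and the prescription change fall on day −14 and the review and enrolment on day 0.
- 15-day run-in: 14 − 15 = −1, so 1 day outside.
- 21-day run-in: 14 − 21 = −7, so 7 days outside.
- 28-day run-in: 14 − 28 = −14, so 14 days outside.

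**5. Stated participation (minor).** In-clinic 2 + transition 1 + home 8 = 11 weeks. The one-week follow-up makes 12, which matches the stated figure. A run-in of at least 2 weeks gives at least 11 + 2 = 13 weeks without follow-up and at least 12 + 2 = 14 with it. Section 6.1 lists what drives actual duration and does not mention the run-in.

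**The case against.** The strongest reply is that recording and reporting are different duties. The enrolment limit in Section 14.4.2 and Table 12 governs reporting to the sponsor. The recording duty in Sections 14.4.1 and 14.5 carries no such limit, contacts for reporting AEs are handed out when the ICF is signed, and the study number is allocated then too. This stands. A reader might infer that run-in events go unrecorded, and the documents do not settle that. They leave the start of recording inconsistent and leave reporting without a rule for this period.

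Other stronger readings also fail:

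- **Exclusions vanish without trace.** They do not. They are recorded as screening failures, each site keeps a screening log, and Section 6.3.1 requires all recruited patients to be accounted for. The eligibility review also covers signs of dehydration and low systolic pressure. However, no AE content is required in the log.
- **The change is imposed.** The run-in is optional, consented and subject to the physician's comparability assessment.
- **The run-in cannot fit the window.** One of exactly 14 days does fit. Only longer ones overflow.
- **The gap can be scaled against the 56 home-phase days.** That is a poor denominator, because AEs are also recorded in the clinic, during training and at follow-up, and only an unknown subset has a run-in.

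None of these replies supplies a date from which run-in events must be reported, or a rule for following them after exclusion.

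**Conclusion.** The point holds as an inconsistency with a practical consequence. For run-in subjects, an AE or SAE arising from the eligibility-driven prescription change need not be reported to the sponsor under the dated rules, and need not be followed if the subject is then excluded. The exposure is at least 14 days per run-in subject, without a stated maximum. The protocol does not give the expected number of such subjects, so the total cannot be sized.

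The conclusion rests on two readings: that the enrolment point for these subjects is the one after the run-in, as Sections 6.2.1 and 6.3.1 say, and that the dated rules in Section 14.4.2 and Table 12 prevail over undated general statements. If a site reads the general statements as covering the run-in, events would be recorded. That the text permits both readings is itself the defect. The between-arm AE comparison, the sample size and the error rates are unaffected. The window and the participation length are minor scheduling points.

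**What to change.** For subjects with a run-in, start AE/SAE recording and reporting at consent, and write the same start everywhere it appears: Table 1 (an AE entry for the run-in), the Visit 1 list in Section 6.4.1, the timelines in Section 14.4.2, and Table 12. Changing Section 14.4.2 alone would leave Table 12 in conflict with it.

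Amend the no-further-follow-up text in both Section 6.2.1 and Section 6.3.1, so that AEs ongoing at exclusion after a run-in are followed to resolution or stabilization, as Sections 6.3.2.1 and 14.4.1 already require for withdrawn subjects.

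List run-in events separately, including those of subjects later excluded, and keep them out of the arm-specific rates in Section 7.1.7.1.

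Reconcile the Visit 1 window and the stated participation of about 12 weeks with a run-in of at least two weeks, for example by dating the run-in as its own period.

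The cost is a small amendment and AE forms for a subset of subjects of unstated size. No treatment rule, sample size or analysis of the primary endpoint changes.

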#### 6.2.2 In-clinic treatment phase for dose determination and safety evaluation

The in-clinic treatment phase will be used to determine the Carry Life® UF dose to be used during the home treatment phase and to enable a safety assessment of the Carry Life® UF glucose dose before using the Carry Life® UF device at home. The in-clinic treatment phase will consist of one 2.27% glucose, 4-hour dwell (PET), and two 5-hour Carry Life® UF treatments (one at 11 g/h glucose and one at 15 g/h glucose). The PET may be performed in the patient's home if the clinic has experience of this practice and a procedure for performing PET at home.

The subjects will use their regular PD prescription the night before each visit, and the PD fluid will be drained at the clinic in the morning before the start of the study treatment. However, the night before the PET, patients who use an icodextrin PD solution overnight will replace the icodextrin solution with a 2.27% glucose solution.

There will be at least one day in between the treatments during the in-clinic treatment phase.

The time and type of breakfast before the in-clinic treatments will be recorded. Any food and fluid intake, as well as urinary output during the visits will be recorded. The subject will be allowed to have a light meal with low glucose content (avoiding sugary carbohydrates) and will only be allowed to drink water and beverages without sugar. Diabetic subjects will record the time for diabetic medications taken before and during the treatment.

AEs, SAEs, and Carry Life® UF device malfunctions will be recorded.

After each in-clinic treatment, the physician may modify the subject's PD prescription for the remainder of the day according to clinical judgement and standard clinical practice to enable adequate fluid removal.

**Visit 2 (2.27% glucose PET)**

- The day before Visit 2, a 24-hour urine collection will be initiated, unless the patient is anuric (<100 ml urine volume/24 hours), and analyzed according to Table 1.
- Patients with an icodextrin prescription for the overnight dwell will replace the icodextrin PD solution with a 2.27% glucose PD solution the night before the PET.
- A 4-hour PET with 2 L, 2.27% glucose PD solution will be performed and the dialysate will be analyzed according to Table 1.
- Blood samples will be taken before treatment for analysis of study base line blood chemistry according to Table 1.
- Venous blood samples for blood glucose measurement will be taken before treatment, at 30 min, at 1 hour and then hourly until the fourth hour (end of treatment) via a peripheral intravenous cannula. If it is not possible to cannulate a subject, samples shall be taken by venipuncture before treatment, at 1 hour and 4 hours.
- Body weight, blood pressure and heart rate will be measured before and after the treatment.

**Visit 3-4 (Carry Life® UF treatments)**

- A 5-hour Carry Life® UF treatments will be performed (Visit 3 using the 11 g/h glucose dose and Visit 4 using the 15 g/h glucose dose).
- A 1.36% glucose PD solution, 1.5–2 L according to the subject's standard prescription will be used for the initial fill and automatic drains will be performed hourly, which means that approximately 180 ml of dialysate will be removed by the system and transferred into a drain bag every hour. The dialysate will be analyzed according to Table 1.
- Venous blood samples for glucose measurement will be taken before treatment, at 30 min, at 1 hour and then hourly until the fifth hour (end of the treatment) via a peripheral intravenous cannula. If it is not possible to cannulate a subject, samples shall be taken by venipuncture before treatment, at 1 hour and 5 hours.
- Body weight, blood pressure and heart rate will be measured before and after the treatments. In addition, blood pressure will be measured in case of clinical symptoms suggestive of hypotension such as lightheadedness, dizziness, feeling faint, tiredness or weakness, change of consciousness e.g., drowsiness, nausea, and cold and clammy skin.

Subjects will be withdrawn from the rest of the study if they:

1. Experience a systolic blood pressure < 100 mmHg where the hypotension is deemed to be caused by hypovolemia due to excessive peritoneal UF.
2. Generate an UF rate higher than 20 ml/kg body weight/treatment.

If the 11 g/h glucose dose Carry Life® UF treatment results in a UF volume of 1.0 L or greater, the 15 g/h glucose Carry Life® UF treatment will not be performed.

Based on the UF volume obtained from the Carry Life® UF treatments the Carry Life® UF dose prescription for the home treatment phase will be determined according to the following criteria:

1. The 15 g/h glucose dose will only be used if both of the following conditions are met:
  - The treatment with the 11 g/h glucose dose achieved a UF volume of less than 1.0 L.
  - The treatment with the 15 g/h glucose dose achieved a UF volume 25% greater than the treatment with the 11 g/h glucose dose.
2. In all other cases the 11 g/h glucose dose will be used.

For example:

- The 11 g/h glucose dose gave a UF volume of 500 ml and 15 g/h glucose dose gave a UF volume of 700 ml UF (40% greater than the 11 g/h glucose dose) à the 15 g/h the Carry Life® UF glucose dose shall be used.
- The 11 g/h glucose dose gave a UF of 500 ml and 15 g/h dose gave a UF of 620 ml (24% greater) à the 11 g/h Carry Life® UF glucose dose shall be used.
- The 11 g/h glucose dose gave a UF volume of 1000 ml à the 11 g/h Carry Life® UF glucose dose shall be used.

Before continuing to the randomization phase, the responsible physician will review the blood chemistry and blood glucose data generated during the in-clinic treatment phase, as well as and the occurrence of a systolic blood pressure of < 100 mmHg or, an UF rate exceeding 20 ml/kg body weight/treatment and confirm that the subject can proceed to the next phase of the study.

**Identification of efficacy evaluation days:** The patient, together with the physician, will confirm the scheduling of the four efficacy evaluation days which will take place during week 2 and week 4 of each study arm in the home treatment phase. For each patient, the efficacy evaluation days should be scheduled on the same day of the week, a Monday, Wednesday or Friday and the same time of the day.

